9.1.2 Serious Adverse Event

An AE is considered "serious" if, in the view of either the Site Investigator or the Sponsor, it results in any of the following outcomes:

- Death.
- Life-threatening AE (i.e., AE in which the subject is at risk of death at the time of the event; it does not refer to an event that hypothetically might have caused death if it were more severe).
- Inpatient hospitalization or prolongation of existing hospitalization.
- Persistent or significant incapacity or substantial disruption of ability to conduct normal life functions.
- Congenital anomaly/birth defect in the offspring of an exposed subject.

A medically important event (i.e., an AE that may not result in death, be life-threatening, or require hospitalization, but may be considered serious when, based upon appropriate medical judgment, the AE may jeopardize the subject and may require medical or surgical intervention to prevent one of the outcomes listed above; examples of such medical events include but are not limited to allergic bronchospasm requiring intensive treatment in an emergency room or at home, blood dyscrasias, or convulsions that do not result in inpatient hospitalizations.)

9.1.3 Suspected Unexpected Serious Adverse Reaction

A suspected unexpected serious adverse reaction (SUSAR) is any SAE that is assessed as both unexpected and, in the view of either the Site Investigator or the Sponsor, as a suspected adverse reaction. The term suspected adverse reaction means that a causal relationship between the medicinal product and the event is at least a reasonable possibility (i.e., there are facts [evidence] or arguments to suggest a causal relationship). The definition of a suspected adverse reaction also covers medication errors and uses outside what is foreseen in the protocol, including misuse and abuse of the product.

An SAE is considered unexpected when its nature or severity is not consistent with the reference safety information (RSI) for the product. The expectedness of all SAEs will be determined by the Sponsor according to the Investigator Brochure.

9.2 Adverse Event Reporting Period

AEs will be monitored continuously during the study and reported from the time that the subject has provided written informed consent through the subject's last day of study participation. Subjects will be queried and events will be assessed at each clinic visit. Further assessments may be done if indicated for evaluating and monitoring the AE(s).

9.3 Recording of an Adverse Event

The Site Investigator is responsible for evaluating all AEs, obtaining supporting documents, and determining that documentation of the event is adequate. He/she is responsible for determining the severity of the AE and its relationship to the investigational drug. The Site Investigator may delegate these duties to Sub-Investigators but must assure that these Sub-Investigators are qualified to perform these duties under the supervision of the Site Investigator.

All AEs will be recorded in the subject's CRF. The detailed description of the event will include appropriately graded severity of the AE and its relationship to the investigational product.

Severity

Severity will be categorized by toxicity grade according to the Common Terminology Criteria for Adverse Events (CTCAE) Version 5.0.

AEs not listed in the Common Terminology Criteria for Adverse Events version 5.0 will be evaluated by using the following criteria:

Grade 1: Mild; asymptomatic or mild symptoms; clinical or diagnostic observations only; intervention not indicated.

Grade 2: Moderate; minimal, local or non-invasive intervention indicated; limiting age-appropriate instrumental ADL (e.g., preparing meals, shopping for groceries or clothes, using the telephone, managing money, etc.).

Grade 3: Severe or medically significant but not immediately life-threatening; hospitalization or prolongation of hospitalization indicated; disabling; limiting self care ADL (e.g., bathing, dressing and undressing, feeding self, using the toilet, taking medications, and not bedridden).

Grade 4: Life-threatening consequences; urgent intervention indicated.

Grade 5: Death related to AE.

Any Grade 3 and 4 clinical laboratory results that represents an increase in severity from baseline will be reported as an AE if it is not associated with a diagnosis already reported on the CRF. A Grade 1 or 2 clinical laboratory abnormality should be reported as an AE only if it is considered clinically significant by the Site Investigator.

In the event of death, the cause of death should be recorded as the AE and reported as a SAE. “Death” is an outcome and not an AE. The term “death” should be reported as an SAE only if the cause of death is not known and cannot be determined. If an autopsy is performed, a copy of the autopsy report should be obtained if possible. The Site Investigator should make every effort to obtain and send death certificates and autopsy reports to Sponsor or designee.

Relationship to Study Treatment

The relationship of the AE to the investigational drug and corticosteroids if administered will be determined by the Site Investigator. The following definitions should be considered when evaluating the relationship of AEs and SAEs to ST-920 treatment.

Not related:

An AE will be considered “not related” to the use of the investigational product or the corticosteroid if there is not a reasonable possibility that the event has been caused by the product under investigation or the corticosteroid. Factors pointing toward this assessment include but are not limited to the lack of reasonable temporal relationship between administration of the product and the AE, the presence of a biologically implausible relationship between the product and the AE, or the presence of a more likely alternative explanation for the AE.

Related:

An AE will be considered “related” to the use of the investigational product or the corticosteroid if there is a reasonable possibility that the event may have been caused by the product under investigation. Factors that point toward this assessment include but are not limited to a positive rechallenge, a reasonable temporal sequence between administration of the product and the AE, a known response pattern of the suspected product, improvement following discontinuation or dose reduction, a biologically plausible relationship between the product and the AE, or a lack of an alternative explanation for the AE.

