3.5 Study Stopping Rules

An SMC with appropriate medical and scientific expertise was appointed to provide safety oversight for the study. The SMC is comprised of external subject matter experts, the study Medical Monitor, Sponsor's Drug Safety Lead, Study Biostatistician, and Site Investigators as appropriate. The SMC will periodically meet during the study and provide recommendations to the Sponsor concerning dosing. The SMC will also convene at any time if an emergent safety issue emerges during the study or one of the stopping rules are met. These include:

- Any one Grade 3 or higher AE with at least a reasonable possibility of a causal relationship to the investigational product
- SAE with at least a reasonable possibility of a causal relationship to the investigational product
- Death of a subject

- Development of a malignancy, with the exception of non-melanoma skin cancers and localized prostate cancer treated with curative intent

The study may also be stopped for any of the following reasons:

- Sponsor, in consultation with the SMC or Regulatory Agency, decides for any reason that subject safety may be compromised by continuing the study.
- Sponsor decides to discontinue development of the investigational product, ST-920.

All data will be evaluated to determine whether changes should be made to the study or if accrual should be continued or halted. If stopping criteria are met, no further dosing of subjects will be performed at that dose level or higher until a substantial amendment is submitted to regulatory authorities for review, and the amendment has been approved by the site Institutional Review Board (IRB)/Independent Ethics Committee (IEC) or equivalent.

Relevant data from other trials sponsored by Sangamo may be shared with the SMC to expand the clinical experience, particularly as it relates to safety and dose, and such data can be used by the SMC to inform its recommendations for the present study.

The SMC may also recommend changes to the dose and enrollment of cohorts based on cumulative safety data from this and other Sangamo sponsored clinical trials that use *in vivo* AAV2/6-based therapy. When no further enrolling or dosing decisions are required of the SMC, the SMC will no longer meet on a regular basis. The Sponsor will continue to review the subject safety data on an ongoing basis.

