11.2.2 Primary Safety Analyses

The primary objective of this study is to evaluate the safety and tolerability of ST-920. Safety assessments will be performed on all subjects. All reported AEs will be coded to a standard set of terms using the Medical Dictionary for Regulatory Activities (MedDRA).

The incidence of TEAEs will be evaluated to address the primary endpoint of this study. A TEAE is any AE with an onset from administration of the study treatment through the last study visit, whether or not it is considered causally related to the study treatment. TEAEs will be

summarized overall and by dose and cohort. For each subject, the maximum reported severity of each AE will be used in the summaries by severity grade. In addition, summaries of all SAEs and AEs related to study treatment will be provided.

Additional safety evaluations will include:

- Routine hematology, chemistry, and liver tests, vital signs, ECG and ECHO
- Serial AFP testing and MRI of liver (or equivalent imaging modality) to monitor for liver mass.

For other safety evaluations, data will be summarized for each time point. Change from baseline values may be calculated for continuous parameters and summarized by time point. Shift-tables may also be constructed for selected parameters.

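### The causality definitions in Section 9.3 are not complements: an adverse event due to the corticosteroid alone is neither related nor not related, so the related-AE summary in 11.2.2 can count it either way

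*Combined protocol and SAP*

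**What the plan says.** Section 9.3, under its paragraph on relationship to study treatment, gives two classes. An event is *not related* "if there is not a reasonable possibility that the event has been caused by the product under investigation or the corticosteroid". The label of the other class names both agents, "to the use of the investigational product or the corticosteroid if there is a reasonable possibility", but the sentence ends by testing one agent only: the event is *related* "if there is a reasonable possibility that the event may have been caused by the product under investigation".

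The same section describes the scope of the judgement in three ways:

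- Both agents: "The relationship of the AE to the investigational drug and corticosteroids if administered will be determined by the Site Investigator".
- ST-920, in the sentence that introduces the definitions: "The following definitions should be considered when evaluating the relationship of AEs and SAEs to ST-920 treatment".
- The investigational product, in the description of what goes into the CRF: "appropriately graded severity of the AE and its relationship to the investigational product".

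Section 11.2.2 then promises that "summaries of all SAEs and AEs related to study treatment will be provided". No summary of corticosteroid-related events is named in 11.2.2 or in the synopsis.

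**The concern.** A binary causality item works only if its two classes are complements. Here one class is defined by two agents and the other by one. An event that an investigator attributes to the corticosteroid and not to ST-920 has no place, so each site must improvise.

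Such events are foreseeable. The protocol expects that ALT rises may occur after AAV2/6 dosing, and Appendix 3 sets out a seven-week corticosteroid course in response. Safety and tolerability are the primary objective, and the related-AE summary is the table a reader would use to separate what ST-920 does from what happens alongside it. If some sites code corticosteroid-only events as related and others do not, that table mixes two definitions and the difference cannot be recovered from the counts.

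**Working it through.** No figure in the plan is at issue, so the check is one of logic. Take the two agents, each either a reasonable cause of the event or not, and apply the 9.3 tests literally. The last column applies the separate causality test in Sections 3.5 and 10.3.

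| ST-920 a reasonable cause | Corticosteroid a reasonable cause | Meets *not related* | Meets *related* | Meets stopping-rule causality |
|---|---|---|---|---|
| No | No | Yes | No | No |
| Yes | No | No | Yes | Yes |
| Yes | Yes | No | Yes | Yes |
| No | Yes | **No** | **No** | No |

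Three of the four patterns are classified. The fourth fails both tests.

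**Would two CRF fields cure it?** The CRF layout is not in the documents, so both layouts need checking.

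- *One combined field.* The fourth pattern is unclassified, as in the table.
- *A field for each agent, with the present definitions.* In the ST-920 field, a corticosteroid-only event still cannot be *not related*, because that class also rules out the corticosteroid as a cause. In the corticosteroid field, the *related* test does not ask about the corticosteroid. The wording fails under either layout.

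**Would adding the missing words cure it?** If the corticosteroid is added to the *related* test, all four patterns are classified. In a single field, however, the fourth row becomes *related* and can no longer be told apart from an ST-920 reaction. Separate items with separate complementary definitions close the gap without merging the causes.

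**What reaches 11.2.2?** The summary is tied to study treatment. Section 9.4 names study treatment and the corticosteroid as two different things, so on that reading a corticosteroid-only event stays out. In 9.3 the same term heads definitions that name both agents, so on that reading the event goes in. Section 11.2.2 does not choose between them.

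**Size.** The documents give neither a rate of corticosteroid use nor a rate of events due to the corticosteroid alone, so no expected count can be computed. What can be stated is the leverage of one subject in a planned expansion cohort of 6: 1/6 = 16.7 percentage points in the proportion with a related AE. This holds only if the subject has no other related AE.

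**The case against.** The best defence is that this is a drafting slip with an obvious intended meaning. The *related* label already names both agents. The opening sentence says corticosteroids are assessed if given, which suits a separate assessment. The definitions are introduced as being for ST-920. Section 11.2.2 counts TEAEs from administration of study treatment, which in a single-infusion trial points to ST-920. On that view the related-AE summary means ST-920, and the literal *related* test agrees with it. Section 11.2 also leaves further detail to the SAP.

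Much of this stands. The ST-920 reading is the more natural one for 11.2.2, and it is the one the fix adopts. It does not rescue the *not related* definition, which a corticosteroid-only event fails under any layout. Nor does it settle what a site will enter when neither class fits.

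Three stronger readings are tempting, and the documents do not support them.

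- *That the stopping rules are distorted.* Those in 3.5 and 10.3 do not use the 9.3 label. The first reads: "Any one Grade 3 or higher AE with at least a reasonable possibility of a causal relationship to the investigational product". The SAE rule carries the same limit. A corticosteroid-only event fails that test whatever 9.3 says. An effect would need a combined flag to be used as the trigger, and no such flag is described.
- *That corticosteroid toxicity would vanish if coded as not related.* The TEAE incidence in 11.2.2 counts events regardless of causality, 9.4 requires every SAE to be reported regardless of relation to either agent, and 7.2 has corticosteroid use recorded as a concomitant medication.
- *That an assumed rate of corticosteroid use gives the number of unclassifiable subjects.* Receiving the corticosteroid is not the same as having an event due only to it. The true number could be zero.

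**Conclusion.** The definitions in 9.3 are wrong as written: one of four cause patterns, corticosteroid alone, is unclassified. That follows from the text and needs no assumption.

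The consequence is confined to the related-AE summary in 11.2.2, which can include or omit such events depending on how a site reads 9.3. This part rests on two conditions the documents leave open: that corticosteroid-only events occur, and that no CRF instruction or SAP text resolves the ambiguity. Neither the direction nor the size of any shift can be derived. The 16.7 points describe one subject's leverage in a cohort of 6 and are not a forecast.

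The primary endpoint, SAE reporting and the stopping criterion as written are not affected. This is a limited defect in a secondary cut of the safety data, worth correcting because the correction is cheap and the table will be read as evidence about ST-920.

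**What to change.** In 9.3, replace the two shared definitions with two separate items, one for ST-920 and one for the corticosteroid where it was given. Define each as an exact complement: a reasonable possibility that this agent caused the event, yes or no. Align the sentences in 9.3 on scope and on CRF content with these items.

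In 11.2.2 and the synopsis, state that the related-AE summary uses the ST-920 item, which also matches the causality wording already in 3.5 and 10.3. Add a separate table of corticosteroid-related AEs. Use study treatment in one sense throughout.

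The cost is corrected wording in 9.3, one eCRF item if it is not already there, and one extra table. If subjects have already been assessed under the present wording, the sponsor should check how sites coded corticosteroid-attributed events before the related-AE table is produced.

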9.4 Serious Adverse Event Reporting

All SAEs, whether or not considered to be related to the administration of study treatment or the corticosteroid, must be reported immediately to Sponsor’s designee, Medpace Clinical Safety, on an SAE Report form within 24 hours of the Site Investigator’s awareness.

MedPace Clinical Safety SAE Report Notification:

Email: [contact]

[contact], dial 3 or [contact], dial 3 or [contact]

[contact] or [contact]

Completion Guidelines of the SAE Report Form should be referred to when completing the SAE Report Form. Medpace Clinical Safety will query the Site Investigator regarding any further information or documentation that is required for a complete case report. Follow-up reports must be submitted within 24 hours from the time that the additional information becomes available. All SAEs must be followed with appropriate medical management until resolved or stabilized.

The reporting period for all SAEs is from subject consent through the last study visit.

The Site Investigator is responsible for promptly notifying the IRB/IEC or equivalent in accordance with local regulations of all SAEs.

9.5 Suspected Unexpected Serious Adverse Reaction Reporting Obligations

The Sponsor or its designee will submit SUSAR reports to appropriate regulatory authorities (including Competent Authorities in all Member States concerned), Ethics Committees, and Site Investigators as per local laws and regulations. Fatal and life-threatening SUSARs will be submitted no later than 7 calendar days of first knowledge of the event and follow-up information submitted within an additional 8 days. All other SUSARs will be submitted within 15 calendar days of first knowledge of the event.

Site Investigators are required to report any urgent safety matters to Sponsor or its designee within 24 hours. Sponsor or its designee will inform the regulatory authorities, ethics committees, and Site Investigators of any events (e.g., change to the safety profile of the study treatment, major safety findings) that may occur during the clinical trial that do not fall within the definition of a SUSAR but may affect the safety of subjects participating in the clinical trials, as required, in accordance with applicable laws and regulations. The reporting period for urgent safety issues is the period from the signing of the Informed Consent Form (ICF) through the last study visit.

The Site Investigator will notify the IRB/IEC or equivalent of SAEs and urgent safety matters, in accordance with IRB/IEC or equivalent requirements and local laws and regulations. A copy of this notification must be provided to Sponsor or its designee.

9.6 Pregnancy Reporting

Pregnancies of female subjects and pregnancies of male subjects' partners occurring during this study are to be reported to Medpace Clinical Safety on the Pregnancy Reporting Form, as per reporting details above in [Section 9.4](#). In general, it is expected that pregnancies are reported in the same timeframe as SAEs (i.e., within 24 hours of awareness by the site). The course of all pregnancies will be followed to partum at minimum. Congenital abnormalities/birth defects in the offspring of subjects should be reported as an SAE if conception occurred during this study.

Consent will be collected from the pregnant partner as per local country requirements before any data is collected.

9.7 Overdose Reporting

Overdose refers to the administration of a quantity of a medicinal product given per administration or cumulatively (accidentally or intentionally), which is above the maximum recommended dose according to the protocol. For this study, administration of the investigational medicinal product, ST-920, in excess of the protocol defined dose is required to be reported within 24 hours of awareness, regardless of whether the overdose is associated with clinical sequelae. The Investigator must complete an Overdose Report Form and submit to Medpace Clinical Safety, as per [Section 9.4](#) above.

10 SUBJECT WITHDRAWAL/DISCONTINUATION, AND SAFETY MONITORING COMMITTEE

10.1 Subject Withdrawal and Discontinuation from Study

Subjects may withdraw or should be discontinued from study for any of the following reasons:

- Request by the subject to withdraw.
- Request of Sponsor or primary care provider if he or she thinks the study is no longer in the best interest of the subject.
- Subject judged by the Site Investigator to be at significant risk of failing to comply with the provisions of the protocol as to cause harm to self or seriously interfere with the validity of the study results.
- At the discretion of the IRB/IEC or equivalent, Office for Human Research (OHR), regulatory authority (e.g. FDA/ Medicines and Healthcare products Regulatory Agency [MHRA] or equivalent), Site Investigator, or Sponsor.

Subjects who, after dosing, discontinue from the study prematurely or are withdrawn from the study will be asked to return to the study site for an early termination visit (ETV). Subjects will be strongly encouraged to continue and comply with follow-up safety evaluations. If a subject withdraws consent or discontinues from the study post-study treatment, a conference between the Site Investigator and Medical Monitor will take place to ensure that the subject understands the importance of the study follow-up and that the study treatment cannot be reversed even if a subject drops out of the study follow-up. If the subject agrees, a reduced follow-up testing schedule may be arranged including telephone call and safety labs to assess treatment-related AEs and disease status. See the Schedule of Events ([Appendix 1](#)) for a list of assessments and procedures performed during the ETV.

